***k) Lower leg skin biopsy (Specific phenotyping but OPTIONAL for a small proportion of patients).***

Skin biopsy together with clinical examination is the gold standard for diagnosing HIV-SN in the clinical setting. This study attempts to use non-invasive means for defining HIV-SN based on examination findings and patient history, using a validated tool. Skin biopsies in a small proportion of patients with extreme phenotypes would allow for comparison with other measures obtained in this study such as NCS, genetic testing and cognitive function which have not been assessed in the context of skin biopsy previously. Biopsies will be taken, fixed and analysed using immunohistochemistry as per the European Federation of Neurological Societies guidelines and biochemical analysis may also be performed. Biopsies will be stored at Chelsea and Westminster Hospital until the end of the study, after which they will be transferred to an HTA approved Tissue Bank.

It is anticipated that up to 30 patients out of the cohort of 200 will undergo skin biopsy and this will be an optional section on the consent form. Patients will be excluded if they are known to be coagulopathic or if they are taking anti-coagulant medication or if they have an allergy to local anaesthetic. They will be given an information leaflet and contact details should there be a problem with bleeding or infection.

### **3.4 Study Outcome Measures**

The aim of the HIV-POGO study is to phenotype a cohort of HIV positive patients with and without HIV-SN and to identify factors associated with neuropathy and, in patients with neuropathy, factors associated with neuropathic pain. It is anticipated that genetic analysis will show differences between the phenotyped groups. We also aim to elucidate any neurocognitive impairment in the cohort and to examine whether there is any correlation with the HIV-SN phenotype or with how pain is reported.

## **4. Participant Entry**

### **4.1 Pre-registration evaluations**

All adult patients aged 18 years or older, attending HIV or chronic pain clinics at St Stephens Centre and Chelsea and Westminster hospital, or partnered clinics, will be invited to participate. Their eligibility for inclusion in the trial will be assessed with a brief questionnaire and those eligible will be offered patient information on the study.

### **4.2 Inclusion criteria**

- Aged 18 years or older
- HIV positive

### **4.3 Exclusion criteria**

- Pregnancy
- Refusal to consent, including for genetic analysis

- Pain ≥4 on NRS due to a pathology other than HIV-SN
- Co-incident severe CNS disease (as determined by the investigator) including a diagnosis of dementia
- Co-incident major psychiatric condition (DSM V criteria[64]: Depression 296.30-36 and Anxiety 300.0-3/21-23/29)
- Limited English language skills as unable to complete questionnaires

#### **4.4 Withdrawal criteria**

If a patient wishes to withdraw from the study, including their data and blood, they can do so at any stage during the protocol. This will not have any effect on their treatment or inclusion in future studies.

#### **5. Adverse Events**

This is an observational study and we are not expecting any adverse events (AE). The only potential anticipated AE would arise from the complications of phlebotomy. Any AEs will be recorded in a AE log and securely stored. Any serious AEs will be reported to the Chief Investigator (AR) within 24 hours. If the SAE was related to the study or occurred unexpectedly, it will be reported to the Sponsor and REC within 15 days.

#### **6. Assessment and Follow up**

Patients will be given the contact details for the Chief Investigator and the investigator conducting the appointment if they have any concerns in the period following the study.

The study will be complete one year after the 200th patient has completed their clinical appointment. This is to allow for further contact with the patient for clarification of information during the analysis phase.

#### **7. Data storage and Data Analysis**

##### **7.1 Data Management**

All data will initially be collected on paper case report forms (CRF). Subjects will be given a study specific identification number that will be used on the CRFs. Therefore no patient identifiable data will be entered on the CRFs. An anonymization log will be stored in the trial master file (TMF) as well as the original completed CRFs; the TMF will be kept in a locked room at Chelsea and Westminster Hospital.

Study information from the paper CRFs will be transcribed onto a password-protected database. Any patient identifiable data will be stored on NHS computers at Chelsea and Westminster Hospital. Such computers require password access and are only accessible to staff. Only anonymized data will be stored on a secure Imperial College computer at Chelsea and Westminster Hospital. Only the research team for this study will have access to this computer.

Relevant data will be shared with deCODE as collaborators, using a secure, encrypted database

##### **7.2 Statistical Analysis**

Statistical advice was sought from deCODE genetics statisticians with regards to sample size and analysis.

#### Genetic Analysis

Single nucleotide polymorphisms (SNPs) that show significant association to defined neuropathic pain phenotypes after genome-wide adjustment will be validated in several independent case-control groups. The validation of the associated signals identified in the GWA study is essential, as successful validation in additional groups would substantially increase our confidence in the associations observed. It will also allow us to determine if an allelic frequency is significantly different between cases and controls, since the familial correction factor will be much less than in the discovery cohort. These single-marker association studies will be analyzed, including adjustment for any familiality in patients or control groups. The p-values in each cohort will be adjusted by Bonferroni correction for number of markers tested or by randomization of phenotype procedure.

In those regions where we observe genome-wide significant associations to neuropathic pain phenotypes that are validated in a second set of independent samples, we intend to select additional markers for genotyping in order to refine the observed association signal and search for possible functional variants.

Re-sequencing will be done to screen for the actual mutation and/or to identify haplotypes that are rarer and have higher risk (for diagnostic purposes). The sensitivity of this method may allow us to detect different frequencies of rare variants such as 3% vs 10% in the general population between patient and control pools. Variants that show association to the phenotypes selected will be converted to a SNP assay and rerun on the entire sample set of the selected phenotype and controls for confirmation of the signal.

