## 1.2 Genetic Risk Factors

Thirdly, little is known about the genetic influences that may predispose an individual with HIV to develop a painful sensory neuropathy. So far, no genome-wide association studies have been published on HIV-SN. Instead, genetic investigation has focused on identifying 'candidate genes' that have been highlighted as being important in the pathophysiology of the disease. Research has focused on genes involved in mitochondrial function, as a potential mechanism for the neurotoxicity of NRTIs, and on genes involved in the inflammatory response, as a mechanism for direct viral-induced neuropathy.

A certain haplotype, involved in the electron transfer chain, has been identified in mitochondrial DNA as being a risk factor for the development of HIV-SN in Europeans on cART [18, 19], but only limited studies have been conducted in African ethnic groups. Some studies have also shown a link between polymorphisms of nuclear DNA, involved in the transcription of mitochondrial DNA [20]. Polymorphisms in the promoter region of the TNF $\alpha$  gene and the untranslated region of the IL12 $\beta$  gene have also been linked to an altered risk of developing HIV-SN in Europeans [21]. In general, very little is known about any genetic associations in the African and Asian populations.

Even less is known about what genetically predisposes patients with HIV-SN to develop neuropathic pain. Currently only the GTP cyclohydrolase 1 (GCH1) gene, involved in the production of pronociceptive molecules, has been shown to have an association with HIV-SN related pain [22]. Therefore, more work remains to be done to identify the genetic and epigenetic influences in the cART era and in different ethnic groups.

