### ***The NeuroPain research group***

This study is part of the NeuroPain Study Group investigating neuropathic pain and endogenous analgesic mechanisms through a broad range of animal and human studies. Imperial College London is NeuroPain Partner 11, and this protocol is part of Work Package 7 in this study. Work Package 7 incorporates four partner groups. One group in Helsinki will be co-ordinating a phenotyping programme for patients following mastectomy that are at risk of chronic post-surgical pain. Another group, based in Berlin, will be conducting a similar protocol with another cohort of HIV patients. All three centres will send blood for exome wide sequencing to deCODE in Iceland and there is consensus between the groups for the core phenotyping of patients.

All three European patient cohorts are to be incorporated as 'replication cohorts'; this is because deCODE already has large amounts of genetic information from previous work on pain syndromes and other disease states. From this information they can apply targeted analysis of the NeuroPain patient cohorts. This also means that the large population numbers usually required for genetic studies are not required.

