#### **3.2 Questionnaire booklet**

Patients will be asked to complete a series of questionnaires given to them at their appointment. They will be asked to post them back to the research group within 2 weeks and will be sent a reminder by text if the questionnaires are not received after 3 weeks. The majority of these scales are part of the 'core phenotyping', which has been agreed across different pain cohorts within the NeuroPain study, and with deCODE. These are described as 'core' phenotyping in the protocol. Some are specific to this HIV cohort and are described as 'specific' phenotyping. Questionnaires are expected to take approximately 45 minutes to complete. The questionnaires to be used have been summarised below.

Questionnaire	Time taken to complete (minutes)	Core or specific phenotyping
DAPOS : Depression Anxiety Positive Outlook Scale	3	Specific
HADS : Hospital Anxiety and Depression Scale	5	Core
BPI : Brief Pain Inventory	5	Core
NPSI : Neuropathic Pain Symptom Inventory	5	Specific
SF-36 : Quality of life index	10	Core
ISI : Insomnia Severity Inventory	3	Specific

TIPI : Ten Item Personality Inventory	3	Specific
PCS : Pain Catastrophizing Scale	5	Core
EMQ: Everyday Memory Questionnaire	5	Specific

Table 1. Summary of post-appointment questionnaires

*a) Basic Psychological Assessment*

- **The Depression Anxiety Positive Outlook Scale (DAPOS) (specific)** will be conducted as the confounding effect of psychological conditions are well recognised in neuropathic pain [39]. This scale has been validated in chronic pain populations and incorporates positive, as well as negative features, which are commonly associated with pain syndromes. Its use will retain backwards compatibility with the data from the HIV-PINS study, samples from which will be also genotyped by deCode within NeuroPain. It is important to recognise depression, as it may be that patients who are depressed are more likely to have pain, or that those with pain become depressed as a consequence of it [40, 41]. It may also be that patients with HAND have higher rates of depression.
- **The Hospital Anxiety and Depression Scale (HADS) (core)** will be used as another measure of anxiety and depression [42]. This is to enable coherence with previously collected data by deCODE and will also allow a direct comparison with DAPOS data in HIV patients.

*b) Quality of Life*

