Patients will be given a body map to illustrate any sites of pain, and the 7-item DN4-i (Douleur Neuropathique 4-interview) interview will be conducted to identify the probability of the patient having neuropathic pain. A score of  $\geq 3$  out of 7 from the patient reported outcome section of the DN4-i will be used as a positive diagnosis of neuropathic pain [57] as this cut-off has been shown to have sensitivity of above 80% in neuropathic pain conditions[58].

Patients will also be asked to indicate the areas that they experience pain. Symptoms must also be in a neuroanatomically plausible distribution, which could be attributable to HIV-SN; for example in a distal, symmetrical distribution. A QUESTOR legend for body areas will be used for this. Both a score of  $\geq 3$  on DN4-i and a plausible anatomical distribution will be required for definition of HIV-SNP.

*f) Neurocognitive Assessment*

- Although full neuropsychological testing is the gold standard for the diagnosis of HAND [60], it is very time consuming and requires specialist delivery which is not universally available. It is also used for the diagnosis of HAND rather than the measurement of it,

and such quantification of the disorder is important for this study, and for longitudinal follow up of patients. One computerised battery of tests (CogState) has been studied in HAND and has been shown to have a positive predictive value of 81%[61]. It also appears to be sensitive enough to monitor changes in ARV therapy and mirrors structural changes identified on MRS[62]. It includes eight tasks conducted with a computer screen and keyboard. There is a 15 minute 'training session' and the test takes approximately 20 minutes. It assesses eight attention, memory and executive function domains (**specific phenotyping**).

- A baseline level of intelligence quotient, such as the National Reading Test has not been included as it is not a longitudinal study and would not accurately assess IQ in such a multicultural population where English is frequently not the first language.
- A subjective measure of cognitive function will also be performed using the Everyday Memory Questionnaire (EMQ). This provides a patient reported measure of memory and attention to compare with the objective computerised measure.

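### The single-marker tests adjust for familiality but not for ancestry in a multicultural cohort, and neither multiplicity option removes the shift that an ancestry imbalance would cause.

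*Combined protocol and SAP*

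**What the plan says.** Section 7.2, Genetic Analysis, is the only description of the replication test. On structure it says "These single-marker association studies will be analyzed, including adjustment for any familiality in patients or control groups". On multiplicity it says the p-values in each cohort will be "adjusted by Bonferroni correction for number of markers tested or by randomization of phenotype procedure". It does not say that the randomisation is restricted in any way. No section mentions ancestry, ethnicity, principal components, genomic control or ancestry-matched controls as part of the analysis.

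Other sections bear on who is tested:

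- Section 3.3 f) Neurocognitive Assessment omits a reading-based IQ test because of "such a multicultural population where English is frequently not the first language".
- Section 4.2 has two inclusion criteria, "Aged 18 years or older" and HIV positive. Section 4.3 excludes limited English but sets no ancestry limit.
- Section 1.2 reports associations mainly in Europeans and says work remains to "identify the genetic and epigenetic influences in the cART era and in different ethnic groups".
- The last part of section 7.2 says that variants found in Iceland will be tested for association with painful HIV neuropathy in this group of 200.
- Section 3.3 a) records ethnicity but gives it no role in the analysis. Under The NeuroPain research group, "All three centres will send blood for exome wide sequencing to deCODE in Iceland".

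**The concern.** Familiality is relatedness within a sample. Ancestry imbalance between the groups is a different matter. If one ancestry is over-represented among patients with neuropathy (or pain) and also carries the tested allele more often, the allele frequencies differ even though the variant does nothing.

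The plan's two multiplicity devices do not address this. Bonferroni lowers the threshold but leaves the statistic centred in the wrong place. Unrestricted shuffling of phenotype makes ancestry independent of phenotype in the reference distribution, so that distribution omits the shift present in the observed data.

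At stake is a false validation in HIV neuropathy or its pain, in a cohort whose stated genetic purpose is replication.

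**Working it through.** **The plan's own figure.** The only computed figure in section 7.2 is the power of an example with 1100 subjects and 5000 controls at risk ratio 1.6. Take the case allele frequency as p×RR/(p×RR+1−p), R² = 0.8 as a sample-size factor, and an assumed two-sided alpha of 5×10⁻⁸ (none is stated). Power is then 94.7% at 15% frequency and 98.9% at 20%, consistent with the plan's figures of over 90% and more than 98%. The concern does not depend on this.

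**Inputs from the documents.** 200 patients (section 3.1); HIV-SN prevalence about 40%, and 38% to 90% of those affected in pain (section 1). Hence 0.40×200 = 80 v 120 for neuropathy, and 30 v 50 to 72 v 8 for pain within neuropathy.

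**Assumed.** Two ancestries, their shares, allele frequencies of 20/30, 15/35 and 20/50% by ancestry, 10 markers (threshold 0.05/10 = 0.005), and comparators drawn from within the cohort.

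**Formula.** With second-ancestry shares w₁ and w₀ in the two groups and allele frequencies f_A and f_B, the mean allele count differs by 2(w₁−w₀)(f_B−f_A) when the variant has no effect.

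**Worked case: 28/80 v 18/120, frequencies 20% v 50%.**

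- Shift: 2×(0.35−0.15)×0.30 = 0.12.
- Variance used by the trend test (pooled share 46/200 = 0.23): 0.77×0.32 + 0.23×0.50 + 0.60²×0.23×0.77 = 0.425. Standard error: √(0.425×(1/80+1/120)) = 0.0941. Shift in z: 0.12/0.0941 = 1.275.
- Actual SD given the ancestry counts: √(0.383/80 + 0.347/120) = 0.0876, a ratio of 0.931 to the standard error.
- Error at 0.05: P(Z > (1.960−1.275)/0.931) = P(Z > 0.736) = 23.1%. At 0.005: P(Z > (2.807−1.275)/0.931) = 5.0%.

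Simulation (Armitage trend test, 200,000 null replicates, fixed ancestry counts) gives 23.1% and 4.9%.

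**All cases, simulated error per marker (%), frequencies 20/30, 15/35, 20/50.**

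| Groups | Second-ancestry counts | At 0.05 | At 0.005 |
|---|---|---|---|
| 80 v 120 | 20 v 30 (equal shares) | 4.7, 4.0, 3.3 | – |
| 80 v 120 | 24 v 24 (30% v 20%) | 5.5, 6.6, 7.9 | 0.56, 0.82, 0.98 |
| 80 v 120 | 28 v 18 (35% v 15%) | 7.5, 15.4, 23.1 | 0.96, 2.78, 4.93 |
| 30 v 50 | 9 v 10 (30% v 20%) | 5.2, 5.4, 5.1 | – |
| 30 v 50 | 10 v 8 (33% v 16%) | 5.7, 7.7, 8.8 | 0.60, 0.95, 1.11 |
| 72 v 8 | 22 v 2 | 4.1, 3.3, 2.8 | – |
| 72 v 8 | 25 v 1 | 4.0, 3.6, 4.4 | – |

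Repeat runs agreed within about 0.4 points. An ancestry-stratified score test gives 4.9-5.0% and 0.4-0.5% in the 80 v 120 and 30 v 50 cases. With equal shares the unadjusted test is conservative, because its variance includes the between-ancestry part.

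**Phenotype randomisation at 0.05, frequencies 20% v 50%** (10,000 replicates, 999 permutations). For 28/80 v 18/120, unrestricted 20.7% and within strata 4.4%. For 10/30 v 8/50, 7.3% and 3.9%.

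**A second method.** An allelic test on 80 v 120, with ancestry drawn at random and frequencies 40% v 15%, gives 10.1% at shares 35% v 25% and 23.2% at 40% v 20%. At the 0.005 threshold these are 1.6% and 5.9%. At 40% v 20%, unrestricted permutation gives 20.2%, and permutation within ancestry 4.2%.

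**External controls.** Section 7.2 does not define the control groups. With 200 cases against an assumed 5000 controls, shares 30% v 5%, the allelic test rejects 22.5% of the time (frequencies 30% v 20%) to 87.6% (40% v 15%).

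**The case against.** The strongest reply is that the harm is assumed. The documents show no ancestry imbalance and give no allele frequencies, and with equal shares the trend test is conservative. The 23.1% case is extreme: it implies HIV-SN in 28/46 = 61% of one ancestry and 52/154 = 34% of the other. Section 1's nearest contrast is about 40% (developed world) v 56% (Malawi, on stavudine-based treatment, so not an ancestry contrast). Taken at face value with an assumed 25% share, it gives 0.14/0.44 = 32% v 0.11/0.56 = 20%, close to the row showing 5.5-7.9%. The contrast nearest the stated replication, pain within neuropathy, moves little. All of this stands, and it is why the size is left open. Neuropathy v no neuropathy is, however, also a stated aim (section 3.4), and external controls could be worse.

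The text says that the adjustments include familiality, so the list is not closed. The familial correction factor is undefined, and deCODE statisticians gave advice. That leaves room for an ancestry method but does not state one, and the text ties the factor to familiality. The protocol also speaks of European patient cohorts, but this reads naturally as the location of the centres.

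Other cohorts buffer a false signal. Section 7.2 lists over 12,000 other chronic-pain patients. Within NeuroPain, "Another group, based in Berlin, will be conducting a similar protocol with another cohort of HIV patients", and there is the HIV-PINS study, "samples from which will be also genotyped by deCode within NeuroPain". This limits the consequence but does not correct the p-value in this cohort, and the plan adjusts p-values cohort by cohort.

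Direction also matters. In the 23.1% case almost all rejections lie on the side of the shift. A rule requiring the Icelandic direction (none is stated) would remove almost all of them if the shift opposes that direction, and almost none if it agrees.

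**Conclusion.** The concern holds in its conditional form. The plan states a test and a randomisation procedure that give wrong p-values if ancestry is unbalanced between the compared groups and the allele frequency varies by ancestry. Neither multiplicity option repairs this. The mechanism follows from the text; the size does not. Under the assumed within-cohort examples, the error at nominal 5% runs from none or slight (pain contrast, 2.8-8.8%) to 5.5-23.1% (neuropathy contrast, unequal shares). The upper end needs a marked imbalance and a large frequency difference. Confidence is medium, because the ancestry mix and the comparators are not given. The change is worth making because it is cheap and an imbalance cannot be ruled out in advance.

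**What to change.** In section 7.2, Genetic Analysis, state that:

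1. Each single-marker test adjusts for familiality and for ancestry, using leading genetic principal components from the planned exome-wide sequencing, or the ethnicity recorded under section 3.3 a) as fallback.
2. Any randomisation of phenotype is done within ancestry strata.
3. Where a compared group is small, a stratified or exact test is used, or only one or two components.

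**Cost.** Wording only; no new data are needed. The information lost to one two-level stratum is 1 − (within-stratum phenotype variance ÷ total). For 28/80 v 18/120 this is 1 − (28×18/46 + 52×102/154)/(80×120/200) = 1 − 45.4/48 = 5.4%. The other imbalanced examples give 1.3% (24/80 v 24/120), 1.3% (9/30 v 10/50), 4.0% (10/30 v 8/50) and 2.0% (25/72 v 1/8). Several components would cost more; that cost was not calculated, and the fit could be unstable if a group is as small as about 8, hence item 3.
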